3.2 Rationale for study design

The subject population will be described in more detail in Section 4 below.

The two visit Screening Period is designed to allow for both (1) washout of prohibited medications, and [REDACTED]

The randomized, blinded, parallel-group design used in this study is based on the primary focus of this study, which is to estimate the difference in clinical response between either remaining on 150 mg or escalating to 300 mg of secukinumab after not achieving a measured state of inactive disease at the Week 12 and Week 16 time points. The responder status at Week 12 and Week 16, as well as the primary objective at Week 52 is determined with the validated ASDAS clinical scoring measure of disease activity status which will establish patients who score within the “inactive disease” classification of this measure (a total score of < 1.3). Week 52 has been selected as the primary analysis time point to allow sufficient time (36 weeks) for a clinical response to be observed following dose escalation to 300 mg at Week 16 vs those patients who remain on 150 mg for the entire 52-week period.

Following the Week 16 visit, randomized inadequate responder patients and investigators will be blind to the dose of secukinumab through the use of a matched placebo injection (identical in appearance) in the 150 mg s.c. group. The blinding of the secukinumab treatments (150 mg or 300 mg) will allow for an evaluation of a potential dose-response of the 150 mg and 300 mg secukinumab doses on both efficacy and safety outcomes.

Responder patients, those who achieve ASDAS inactive disease at Week 12 and Week 16, will continue on secukinumab 150 mg to evaluate the longer-term treatment response up to Week 52. To support the integrity of the blind for the randomized inadequate responder group, the responder patients will also be dose blinded between Week 16 and Week 48 by receiving a single matching placebo injection to their secukinumab 150 mg injection. Thus, all responder and inadequate responder patients will be blinded to dose and will receive two matched injections every 4 weeks. While the responder group is not the primary focus of this study, this subgroup will provide meaningful exploratory analyses of the clinical characteristics and duration of response in patients who achieve a high-level efficacious response to secukinumab at Week 16.

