## **2.4 Treatments (study treatment, rescue medication, concomitant therapies, compliance)**

### **2.4.1 Study treatment / compliance**

#### **Study Treatment**

The summaries by treatment group will be performed by the actual treatment received (as follows) for every visit until Week 16.

Treatment groups in Treatment Period 1:

- Secukinumab 150 mg

In Treatment Period 2, the summaries by treatment group will be performed by the actual treatment received (as follows) for every visit up to Week 52, including patients who switched at Weeks 16.

Treatment groups in Treatment Period 2:

- Secukinumab 150 mg - 300 mg (IR)
- Secukinumab 150 mg - 150 mg (IR)
- Secukinumab 150 mg – 150 mg (R)

where, R: Responders and IR: Inadequate Responders

Treatment groups in entire treatment period:

- Secukinumab 150 mg

- Secukinumab 300 mg

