### **Duration of exposure**

The duration of exposure (in days) will be summarized by means of descriptive statistics for the Enrolled Set, the Responder Set, and each treatment group for the Safety Set. In addition, the number of subjects with exposure of at least certain time thresholds will be displayed (e.g. any exposure,  $\geq 1$  week,  $\geq 2$  weeks,  $\geq 3$  weeks,  $\geq 4$  weeks,  $\geq 8$  weeks, etc.).

For Treatment Period 1, the end date for the calculation of duration of exposure will be the earlier of:

- Date of last injection in Treatment Period 1 + 84 days, and
- Date of first injection in Treatment Period 2

For Treatment Period 2, the end date for the calculation of duration of exposure will be the date of last injection in Treatment Period 2 + 84 days.

For entire treatment period, the end date for the calculation of duration of exposure will be the date of last injection + 84 days.

For patients with death as an event, end date for calculation of duration of exposure will be the date of death if it is earlier than the date of last injection + 84 days.

Duration of exposure (years) = duration of exposure (days) / 365.25

Duration of exposure (100 patient years) = duration of exposure (years) / 100

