## **2.8 Safety analyses**

The safety analysis will be performed on Enrolled Set for Treatment Period 1 and on Safety Set for Treatment Period 2.

All listings and tables will be presented for Treatment Period 1, for responders who enter Treatment Period 2, and by treatment group for inadequate responders who are randomized.

The analyses for treatment-emergent adverse events, serious adverse events and risk based on adverse events will be summarized. Safety analyses will be performed on treatment received or actual treatment as described below:

- The actual treatment or treatment received for summaries of safety data will differ from the treatment assigned at randomization only if a subject received the wrong treatment during the entire study.
- For those patients who received not the treatment randomized, i.e., who received erroneously the wrong treatment at least once, an additional AE listing will be prepared displaying which events occurred after the treatment errors.

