### 2.8.1 Adverse events (AEs)

The crude incidence of treatment emergent adverse events (TEAEs) will be summarized by primary system organ class (SOC) and preferred term (PT) for Treatment Period 1 and Treatment Period 2.

Treatment-emergent adverse events (TEAEs) are defined as follows:

- For Treatment Period 1, TEAEs are those AEs that started on or after the first dose date of study treatment, or events present prior to the first dose date of study treatment but increased in severity based on preferred term and the earlier of the last dose date in Treatment Period 1 + 84 days or prior to the first dose date in Treatment Period 2.
- For Treatment Period 2, TEAEs are those AEs that started on or after the first dose date of study treatment in Treatment Period 2 and on or before the last dose date + 84 days.

In addition, exposure time-adjusted rates (incidence rate) including 95% confidence intervals will be provided for entire treatment period to adjust for differences in exposure. For the entire treatment period, TEAEs are those AEs that started on or after the first dose of study treatment, or events present prior to the first dose of study treatment but increased in severity based on preferred term and on or before last dose date + 84 days. For summaries over the entire treatment period, patients who switched from secukinumab 150 mg to secukinumab 300 mg will appear in both treatment groups.

Crude incidence rates and exposure-adjusted incidence rates will be graphically presented for all TEAEs and serious TEAEs along with 95% confidence intervals, by system organ class.

Adverse events will be summarized by presenting, for each treatment group, the number and percentage of patients having at least one AE, having an AE in each primary system organ class and having each individual AE (preferred term). Summaries (crude incidences only) will also be presented for AEs by severity and for study treatment related AEs. If a particular AE 'severity' is missing, this variable will be listed as missing and treated as missing in summaries. If a subject reported more than one adverse event with the same preferred term, the adverse event with the greatest severity will be presented. If a subject reported more than one adverse

event within the same primary system organ class, the subject will be counted only once with the greatest severity at the system organ class level, where applicable.

Separate summaries will be provided for

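### Exposure-adjusted adverse-event rates are named only for the entire treatment period, where over half of the planned 150 mg exposure is not the randomised comparator, so they are not a randomised dose comparison

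*SAP*

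**What the plan says.** SAP 2.8.1 plans crude incidence of treatment-emergent events by system organ class and "preferred term (PT) for Treatment Period 1 and Treatment Period 2". For rates per unit of exposure it names a different window: "exposure time-adjusted rates (incidence rate) including 95% confidence intervals will be provided for entire treatment period to adjust for differences in exposure". It then says how dose switchers are handled: "For summaries over the entire treatment period, patients who switched from secukinumab 150 mg to secukinumab 300 mg will appear in both treatment groups".

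SAP 2.4.1 lists the groups. Under "Treatment groups in Treatment Period 2" there are three: inadequate responders moved to 300 mg (150-300 IR), inadequate responders kept on 150 mg (150-150 IR), and responders kept on 150 mg (150-150 R). Under "Treatment groups in entire treatment period" there are two: 150 mg and 300 mg.

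SAP 2.8 says that safety output will be shown for Period 1, for responders in Period 2, and "by treatment group for inadequate responders who are randomized".

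On exposure time, SAP 2.4.1 states: "For entire treatment period, the end date for the calculation of duration of exposure will be the date of last injection + 84 days". SAP 5.4.5 describes the denominator differently, as days on which a dose above zero was given, and takes as numerator the patients with at least one event.

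Protocol 3.2 says that the blinding permits an "evaluation of a potential dose-response of the 150 mg and 300 mg secukinumab doses on both efficacy and safety outcomes".

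**The concern.** The two entire-period columns differ in more than dose.

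- **150 mg:** the first 16 weeks of every treated patient (including early discontinuers, non-responders and those later moved to 300 mg), the responders after Week 16, and the randomised 150 mg arm after Week 16. The run-in is open-label and starts with weekly dosing.
- **300 mg:** only blinded time after Week 16, in patients who stayed on drug for 16 weeks, improved without meeting the responder definition, and were randomised to 300 mg.

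Time on drug and patient selection are therefore mixed with dose. If adverse events are commoner early in treatment, the pooled 150 mg rate is raised and 300 mg looks better than it should. If they become commoner later, the reverse holds. These are the only rates that the SAP describes as adjusted for exposure, and Protocol 3.2 names safety by dose as something the blinded design allows one to examine. A reader who sees two dose columns side by side, each with an interval, is likely to compare them.

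**Working it through.** **1. The plan's own figures.** These are in Protocol 9.8 and SAP 3.

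- Precision: n per arm = 1.96² × (0.20×0.80 + 0.10×0.90) / 0.10² = 96.04, rounded up to 97.
- Number randomised: 270 × 0.90 × 0.80 = 194.4, stated as 194.

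Both reproduce. Neither is disputed; they are used here to size the columns.

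**2. Planned flow.** Of 270 enrolled, 27 discontinue in Period 1, leaving 243. These split into 24.3 responders, 194.4 inadequate responders (97.2 per arm) and 24.3 non-responders.

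**3. Exposure in patient-weeks.** Everyone who enters Period 2 is assumed to complete it, and a switcher's 150 mg time is assumed to end at Week 16. Two ways of counting:

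- **A, to scheduled visits:** Period 2 lasts 36 weeks. Early discontinuers contribute 8 weeks on average (assumed).
- **B, last injection + 84 days (SAP 2.4.1):** Period 2 runs from Week 16 to Week 48 + 12, which is 44 weeks. Non-responders contribute 12 + 12 = 24 weeks. Early discontinuers contribute 8 + 12 = 20 weeks (Week 8 assumed as the average last injection).

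| Component | A | B |
|---|---|---|
| Run-in, all patients | 243×16 + 27×8 = 4,104 | 218.7×16 + 24.3×24 + 27×20 = 4,622.4 |
| Responders, Period 2 | 24.3×36 = 874.8 | 24.3×44 = 1,069.2 |
| Randomised 150 mg, Period 2 | 97.2×36 = 3,499.2 | 97.2×44 = 4,276.8 |
| **150 mg total** | 8,478.0 (162.5 patient-years) | 9,968.4 (191.0 patient-years) |
| **300 mg total** | 3,499.2 (67.1 patient-years) | 4,276.8 (82.0 patient-years) |
| Run-in / responders / randomised arm, share of 150 mg | 48.4% / 10.3% / 41.3% | 46.4% / 10.7% / 42.9% |

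Patient-years use 52.18 weeks per year. On either count, 57–59% of the 150 mg exposure is not the randomised comparator.

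**4. Rate ratio with no dose effect.** Let the run-in event rate be k times the Period 2 rate, with the Period 2 rate the same in all groups. With s the run-in share, the pooled ratio in events per person-time is

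300:150 = 1 / (k·s + 1 − s).

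| k (assumed) | A, s = 0.484 | B, s = 0.464 |
|---|---|---|
| 0.75 | 1.14 | 1.13 |
| 1.00 | 1.00 | 1.00 |
| 1.25 | 0.89 | 0.90 |
| 1.50 | 0.81 | 0.81 |
| 2.00 | 0.67 | 0.68 |

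**5. On the SAP's first-event rate.** SAP 5.4.5 divides patients with a first event by time to first event or censoring. With constant hazards within each period and assumed Period 2 rates of 0.2 to 2 per year, the ratio is 1.14–1.21 at k = 0.75, 1.00 at k = 1, 0.73–0.80 at k = 1.5 and 0.56–0.67 at k = 2. The direction is the same and the departure from 1 is at least as large.

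**6. Restricted to Period 2 by randomised arm.** The groups are 97 against 97 with equal planned exposure: 67.1 against 67.1 patient-years on count A, 82.0 against 82.0 on count B. The ratio with no dose effect is 1.00 for every k.

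**The case against.** The strongest reply is that the randomised safety comparison is already there. Period 2 groups keep the two randomised arms and the responders apart, crude incidence is planned for that period, and 1:1 allocation on one dosing schedule makes planned exposure equal. Crude incidence is then a fair comparison unless dropout differs between arms, and Period 2 exposure is tabulated by group, so a difference would be visible. All of this stands. A reader might infer that the trial's whole dose comparison on safety is confounded; the documents do not support that.

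Other limits also stand:

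- The SAP plans rates with intervals per group. It plans no ratio, difference or test of the entire-period rates, and the safety objective is overall safety and tolerability. The risk lies in how the side-by-side table is read.
- Protocol 3.2 says that the design permits a look at dose-response. It does not promise to demonstrate one.
- The sentence on figures by system organ class names no period and covers crude rates too. One may infer that the exposure-adjusted figure is entire-period, because those rates are named for nothing else, but the text does not say so.
- Nothing says that an event is counted twice. What is missing is a rule assigning a switcher's events and days to one column or the other.

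The general sentence in SAP 2.8 on listings and tables could be stretched to cover exposure-adjusted rates by arm. However, 2.8.1 is the specific provision for those rates, and it names only the entire period.

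**Conclusion.** The point holds in a limited form. As written, the only exposure-adjusted adverse-event rates named are for two columns that are not a randomised comparison, and the randomised 150 mg arm makes up only about 41–43% of the planned 150 mg exposure. That share rests on the planned flow, full completion of Period 2 and an assumed average time for early discontinuers; the two counting rules give nearly the same answer.

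A reader might go further and conclude that the table will make 300 mg look safer. The documents give no adverse-event rates by time on drug, so direction and size are unknown. The ratio could be about 0.81, 1.00 or 1.14 with no dose effect, depending wholly on the assumed multiplier. At a multiplier of 1 the time effect vanishes, and only differences in who is in each column could remain.

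The defect covers the exposure-adjusted rates and any other display that uses the two-group layout. The ClinicalTrials.gov tables in SAP 2.8.1 are planned for the entire period and would take the same two groups, although they are not exposure-adjusted tables. Efficacy analyses and the crude Period 2 safety tables are unaffected. This is a worthwhile, inexpensive improvement in reporting.

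**What to change.** In SAP 2.8.1:

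1. Add exposure-adjusted rates with 95% confidence intervals for Treatment Period 2 by randomised arm (150-300 IR against 150-150 IR), with 150-150 R in its own column.
2. Use these rates for any dose comparison of exposure-adjusted rates and for the exposure-adjusted figure by system organ class.
3. Keep the entire-period two-group rates if wanted, labelled descriptive and non-randomised. State that each event and each day of exposure is assigned to the dose being taken at the time.
4. Use one definition of exposure time in SAP 2.4.1 and 5.4.5.

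The cost is a few lines of SAP text and a re-run of existing programs by period; no new data are needed. The 150 mg intervals will be wider than in the pooled table, because they rest on about 67 to 82 patient-years instead of about 163 to 191. The SAP's last revision is dated after database lock, so the added display should be dated and marked as added at that stage.

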### **2.8.1.1 Adverse events of special interest / grouping of AEs**

Not applicable.

### **2.8.2 Deaths**

Separate summaries and listings will be provided for deaths in each treatment period.

### 2.8.3 Laboratory data

The summary of laboratory evaluations will be presented for three groups of laboratory tests (hematology, chemistry and urinalysis).

Descriptive summary statistics for the change from baseline in Treatment Period 1 and change from Week 16 in Treatment Period 2 to each study visit in respective treatment periods will be presented. These descriptive summaries will be presented by laboratory test and treatment group. Change from baseline (or Week 16) will only be summarized for patients with both baseline (or Week 16) and post-baseline (or post-Week 16) values and will be calculated as:

$$\text{change from baseline} = \text{post-baseline value} - \text{baseline value}$$

$$\text{change from Week 16} = \text{post-Week 16 value} - \text{Week 16 value}$$

For urinalysis and urine pregnancy test, data will be listed by treatment and patient.

QuantiFERON TB-Gold test, serum pregnancy test results and HLA-B27 results will be listed at Screening Visit 2, by treatment and patient.

Shift table will be provided for all laboratory variables to compare a patient's baseline laboratory evaluation relative to observed post-baseline values in Treatment Period 1. The reference laboratory ranges will be used to evaluate whether a particular laboratory test value was within reference range, low, or high for each visit value relative to whether or not the baseline value was within reference range, low, or high. The shifts to the most extreme laboratory test value within the treatment period will be presented (including category "high and low"). These summaries will be presented by laboratory test and treatment group. Similar shift tables will be provided for all laboratory variables to compare a patient's Week 16 laboratory evaluation relative to observed post-Week 16 values in Treatment Period 2.

The following laboratory variables will be analyzed with respect to numerical common terminology criteria for adverse events (CTCAE) grades, given in [Table 2-3](#): hemoglobin (HGB), platelets, white blood cell (WBC) count, neutrophils, lymphocytes, creatinine, total bilirubin (TBL), gamma-glutamyl transferase (GGT), alanine aminotransferase (ALT), aspartate aminotransferase (AST), alkaline phosphatase (ALP), glucose.

**Table 2-3 CTCAE grades for laboratory variables to be analyzed**

CTCAE Term	Grade 1	Grade 2	Grade 3	Grade 4
HGB decreased (Anemia)	< LLN – 100 g/L	< 100 – 80 g/L	< 80 g/L	
Platelet count decreased	< LLN – 75.0 x 10e9 /L	< 75.0 - 50.0 x 10e9 /L	< 50.0 – 25.0 x 10e9 /L	< 25.0 x 10e9 /L
WBC decreased	< LLN - 3.0 x 10e9 /L	< 3.0 - 2.0 x 10e9 /L	< 2.0 - 1.0 x 10e9 /L	<1.0 x 10e9 /L
Neutrophil count decreased	< LLN - 1.5 x 10e9 /L	< 1.5 - 1.0 x 10e9 /L	< 1.0 - 0.5 x 10e9 /L	< 0.5 x 10e9 /L
Lymphocyte count decreased	< LLN - 0.8 x 10e9/L	< 0.8 - 0.5 x 10e9 /L	< 0.5 - 0.2 x 10e9 /L	< 0.2 x 10e9 /L

Creatinine increased*	> 1 - 1.5 x baseline; > ULN - 1.5 x ULN	> 1.5 - 3.0 x baseline; > 1.5 - 3.0 xULN	> 3.0 x baseline; > 3.0 - 6.0 x ULN	> 6.0 x ULN
TBL increased	> ULN - 1.5 x ULN	> 1.5 - 3.0 x ULN	> 3.0 - 10.0 x ULN	> 10.0 x ULN
GGT increased	> ULN - 2.5 x ULN	> 2.5 - 5.0 x ULN	> 5.0 - 20.0 x ULN	> 20.0 x ULN
ALT increased	> ULN - 3.0 x ULN	> 3.0 - 5.0 x ULN	> 5.0 - 20.0 x ULN	> 20.0 x ULN
AST increased	> ULN - 3.0 x ULN	> 3.0 - 5.0 x ULN	> 5.0 - 20.0 x ULN	> 20.0 x ULN
ALP increased	> ULN - 2.5 x ULN	> 2.5 - 5.0 x ULN	> 5.0 - 20.0 x ULN	> 20.0 x ULN
Glucose increased (Hyperglycemia )	> ULN - 8.9 mmol/L	> 8.9 - 13.9 mmol/L	> 13.9 - 27.8 mmol/L	> 27.8 mmol/L
Glucose decreased (Hypoglycemia)	< LLN - 3.0 mmol/L	< 3.0 - 2.2 mmol/L	< 2.2 - 1.7 mmol/L	< 1.7 mmol/L

LLN = lower limit of normal, ULN = upper limit of normal

\*Note: for "creatinine increased" the baseline criteria do not apply

These summaries will be split into hematology and chemistry for study level reports and the pooled summary of clinical safety.

Shift tables will be presented comparing baseline laboratory result (CTCAE grade) with the worst results (expressed in CTCAE grade) during the treatment period analyzed.

Newly occurring or worsening liver enzyme abnormalities will also be summarized based on the event criteria given in [Table 2-4](#) below:

**Table 2-4 Liver-related events**

Assessment	Criterion
ALT	> 3 x ULN; > 5 x ULN; > 8 x ULN; > 10 x ULN, > 20 x ULN
AST	> 3 x ULN; > 5 x ULN; > 8 x ULN; > 10 x ULN; > 20 x ULN
ALT or AST	> 3 x ULN; > 5 x ULN; > 8 x ULN; > 10 x ULN; > 20 x ULN
TBL	> 1.5 x ULN; > 2 x ULN; > 3 x ULN
ALP	> 2 x ULN; > 3 x ULN; > 5 x ULN
ALT or AST and TBL	ALT or AST > 3 x ULN and TBL > 2 x ULN ALT or AST > 5 x ULN and TBL > 2 x ULN ALT or AST > 8 x ULN and TBL > 2 x ULN ALT or AST > 10 x ULN and TBL > 2 x ULN
ALP and TBL	ALP > 3 x ULN and TBL > 2 x ULN ALP > 5 x ULN and TBL > 2 x ULN
ALT or AST and TBL and ALP	ALT or AST > 3 x ULN and TBL > 2 x ULN and ALP < 2 x ULN (Hy's Law)

---

Note: elevated ALP may suggest obstruction as a consequence of gall bladder or bile duct disease; ALP may also be increased in malignancy. FDA therefore terms Hy's Law cases as indicators of pure hepatocellular injury. This does not mean that cases of ALT or AST > 3 x ULN and TBL > 2 x ULN and ALP ≥ 2 x ULN may not result in severe DILI.

---

For a combined criterion to be fulfilled, all conditions have to be fulfilled on the same visit.

The criteria are not mutually exclusive, e.g. a subject with ALT = 6.42 × ULN is counted for ALT > 3 × ULN and ALT > 5 × ULN.

Individual subject data listings will be provided for subjects with abnormal laboratory data.

### **2.8.3.1 Hematology**

Hemoglobin, platelet, red blood cell (RBC), white blood cell (WBC) and differential white blood cell counts will be measured at Screening Visit 2, and Visits 3, 9, 10, 13, 16 and 19.

### **2.8.3.2 Clinical chemistry**

Measured at Screening Visit 2, and Visits 3, 9, 10, 13, 16 and 19, serum chemistry will include glucose, urea, creatinine, total bilirubin, AST (SGOT), ALT (SGPT), GGT, alkaline phosphatase, sodium, potassium, bicarbonate, calcium, phosphorous, total protein, albumin, and uric acid.

### **2.8.3.3 Urinalysis**

Urinalysis will be performed at Visits 3, 7, 9, 10, 12, 14, 16 and 19. Dipsticks will be provided by the central laboratory to the sites for local urinalysis assessments. The urinalysis results for standard parameters such as protein, glucose, blood and WBCs will be recorded in the appropriate eCRF page.

